Patients who are critically ill may require emergency placement of a breathing tube in their mouth and windpipe. The purpose of this breathing tube is to save the patient's life. Usually the treating medical team administers a drug to sedate the patient before the breathing tube is placed. For critically ill patients it is common to choose either etomidate or ketamine to sedate the patient. These drugs are often chosen because they have few effects on the patient's blood pressure and heart rate. Etomidate has some other serious side effects which include interference with the production of steroids by the adrenal glands. Previous studies have suggested that etomidate may cause greater long-term illness and even death because of this side effect. The purpose of the EvK Trial is to evaluate which drug (etomidate or ketamine) is better for patients who are critically ill. We believe that ketamine is associated with improved chance of survival after emergency endotracheal intubation because it does not interfere with steroid production. Because this study involves research of an emergency medical procedure, we have created a comprehensive Community Consultation Plan and Post-Enrollment Notification Plan that meets U.S. Food and Drug Administration regulations for emergency research.

2. Introduction and Purpose:

Patients who are critically ill may require emergency placement of an endotracheal tube. The purpose of the endotracheal tube is to save and sustain the patient's life. Prior to placement of an endotracheal tube, it is common for the supervising medical team to administer a drug intravenously to sedate the patient to make this placement of the tube tolerable. Several drugs are commonly used for this purpose, including etomidate, ketamine and propofol. Both etomidate and ketamine are useful in critically ill patients because they offer relative hemodynamic stability compared to propofol. Ketamine has few, if any, serious long-term side effects.

Etomidate is known to suppress adrenal steroidogenesis, and thereby may place patients at risk for adrenal insufficiency or death (Coursin et al., 2013). A recent Cochrane Collaboration Review concluded that etomidate is associated with increased risk of adrenal dysfunction and multi-organ dysfunction in critically ill patients (Bruder et al., 2015). There is ongoing controversy regarding the routine use of etomidate in critically ill patients.

The **purpose** of the EvK Trial is to compare and contrast the safety of etomidate with ketamine in the setting of emergency endotracheal intubation in critically ill patients. In this study we will randomize patients to receive either etomidate or ketamine. Our **hypothesis** is that ketamine is associated with increased chance of survival in critically ill patients. The proposed **mechanism** of this effect is that ketamine does not affect the adrenal axis. The **specific aim** of the study is to conduct an adequately powered trial suitable to compare etomidate and ketamine in terms of proportions survived at 7-days post-intubation. The **primary endpoint** is survival at 7 days after intubation. **Secondary endpoints** include long-term survival (28-day), Sequential Organ Failure Assessment (SOFA) scores, anesthetic complications, intubating conditions, duration of ventilator support, duration of catecholamine therapy, neurological scores, measures of ICU outcomes, measures of long-term functional status, changes in blood pressure, new diagnoses, and others. Appendix 1 lists primary and secondary endpoints for the study.

3. Detailed Background, Evaluation of Prior Research and Internal QA/QI Data:

Both etomidate and ketamine are standard-of-care for emergency endotracheal intubation, and both are frequently used locally, nationally and internationally. Etomidate is often used at our institution (Parkland Memorial Hospital), based on our last QA/QI survey of our practices (Figures 1 and 2). There is considerable controversy regarding the long-term safety of the use of

etomidate for emergency endotracheal intubation. The largest study to date that evaluated this question (the KETASED Trial, Jabre et al., 2009) randomized patients requiring emergency endotracheal intubation to either etomidate (n=234) or ketamine (n=235). The patients who received etomidate experienced a much-higher frequency of adrenal dysfunction, and a slight but not statistically significant increase in multi-organ dysfunction and mortality. Other published reports echo concerns about etomidate. A sub-group analysis within the CORTICUS Trial (Sprung et al., 2008) (n=99 receiving etomidate, n=403 receiving other agents) found that one dose of etomidate was associated with evidence of adrenal insufficiency and increased mortality (Cuthbertson et al., 2009). Another sub-group analysis from a different clinical trial (Arabi et al., 2010) of cirrhotic patients with septic shock (n=23 receiving etomidate, n=39 receiving other agents) reported increased ICU mortality associated with a single dose of etomidate (Cherfan et al., 2011). A recent meta-analysis incorporating these and other studies concluded that a single dose of etomidate is associated with adrenal insufficiency and increased mortality (Chan et al., 2012).

In late 2014 and early 2015 the Department of Anesthesiology at Parkland Memorial Hospital performed a Quality Assessment/Quality Improvement (QA/QI) project that evaluated techniques and outcomes from emergency endotracheal intubations done by the Anesthesia Code Team (ACT). [REDACTED]

[REDACTED]

[REDACTED]

[REDACTED]

[REDACTED]

[REDACTED]

The purpose of the EvK Trial is to be the largest trial to date that randomizes critically ill patients to etomidate (n=375 patients) versus ketamine (n=375). Additionally, the EvK Trial has been designed to address some of the shortcomings of the KETASED trial. First, the KETASED trial was not powered to detect a difference in mortality, although did find a trend in survival benefit in those patients randomized to receive ketamine. We have designed the EvK Trial to be powered to detect a 10% difference in survival in our patient population (See Section 14 for a discussion of our statistical approach). Second, the primary endpoint of the KETASED trial was the maximum SOFA score in the first 72 hours as the primary endpoint. From our QA/QI data, we believe that a more appropriate endpoint in our patient population is survival at Day 7. Third, the KETASED trial enrolled a large percentage of patients (approximately 70% in each group) who were intubated for “neurological” reasons, and relatively few patients (approximately 10% in each group) who were intubated for shock or sepsis. Prior work has suggested that patients with sepsis and shock are much more vulnerable to the side effects of etomidate. In our QA/QI data, approximately 50% of the patients intubated by the ACT are in shock, and at least 25% have sepsis. This suggests that our patient population is more likely to benefit from use of ketamine compared to the patient population in KETASED.

4. Concise Summary of Project:

The EvK Trial is a prospective randomized clinical trial that will be done at Parkland Memorial Hospital. Individual patients requiring emergency endotracheal intubation will be randomized to receive either etomidate (n=375 patients) or ketamine (n=375 patients). The trial will be conducted by members of our study team and colleagues in the Departments of Anesthesiology, Emergency Medicine, Internal Medicine, Critical Care Medicine, and Surgery, in close collaboration with the Department of Pharmacy. The study will be done exclusively at Parkland Hospital. A provisional list of collaborators and co-investigators is listed on Page 1 of this protocol, and provisional liaison assignments are listed in Appendix 2. The liaisons will help orient their colleagues to the study and study procedures.

Figure 5 shows a block diagram of the flow of patients through the study. Eligible patients will be identified by the participating medical teams (anesthesia team, emergency department, critical care medicine, surgery). Patients will be screened and enrolled by two teams: The Anesthesia Code Team (ACT) and/or the Emergency Department (ED). Pre-randomized envelopes will be included in the emergency airway medication boxes used by the Anesthesia Code Team and the Emergency Department. Alternatively, these pre-randomized envelopes will be immediately available to the aforementioned teams. These envelopes will have inclusion and exclusion criteria printed on the outside. Immediately before administering a sedative medication, the randomization envelope will be opened, and this will determine which drug a patient receives (either etomidate, n=375 patients, or ketamine, n=375 patients). Standard doses of these drugs will be recommended to the treating medical teams (etomidate 0.2-0.3 mg per kg intravenous, ketamine 1-2 mg per kg intravenous). Other therapies, including vasopressors, paralytic agents and other adjunctive agents will be at the discretion of the treating medical and surgical teams. Following randomization, study data will be gathered remotely through the EPIC

Electronic Medical Record. The only subsequent patient contact will involve post-randomization notification of study enrollment, which is discussed below in Appendix 5.

5. Study Procedures:

Figure 5 shows a simplified block diagram for how the study will be conducted.

Individual patients who are in need of emergency endotracheal intubation will be identified by the treating medical or surgical teams, many of whom are co-investigators on this project. For patients in the Emergency Department (ED), the ED team will screen, randomize and enroll the patient. For patients elsewhere in Parkland Hospital, the Anesthesia Code Team (ACT) will screen, randomize and enroll the patient. The ACT and ED teams will have access to the study randomization envelopes and drug boxes. The drug boxes are already in use by the ACT and ED teams. Randomizing a patient in the study will involve opening a pre-printed envelope that will be included with the emergency medication boxes, or will be immediately available to the ACT or ED teams. The envelopes will have printed inclusion criteria (Section 7) and exclusion criteria (Section 8) on the outside to facilitate rapid and accurate screening of patients. The envelopes will contain a card that indicates which drug the patient should receive for sedation (etomidate or ketamine). Recommended doses of these medications will be printed as well (etomidate 0.2-0.3 mg / kg intravenous, ketamine 1-2 mg / kg intravenous). All other medical and surgical management will be at the discretion of the treating team.

Following randomization the ACT or ED team will notify the Principal Investigator by secured internal email or telephone / pager call regarding enrollment of the patient. The study team will conduct the remainder of the study retrospectively by extracting information from the EPIC Medical Record system to fulfill the primary and secondary endpoints of the study. The study will have no impact on the patient's medical or surgical management, or subsequent care,

beyond the initial choice of sedative agent. Formal notification of study enrollment, in accord with U.S. Food and Drug Administration regulations, will be performed by the PI and / or Co-Investigators. A final, written report(s) of the study results will be published in an open, public forum. No Protected Health Information (PHI) will be disclosed. The written report(s) will include results of the primary and secondary endpoints, in addition to study methodology. We will likely also publish an assessment of our Community Notification Plan (Appendix 5).

6. Sub-Study Procedures:

None.

7. Criteria for Inclusion of Subjects:

A) Adult patient requiring emergency endotracheal intubation at Parkland Memorial Hospital.

8. Criteria for Exclusion of Subjects:

A) Children (<18 years old).

B) Women who are known to be pregnant.

C) Any patient who has been previously randomized in the EvK Trial.

D) Patients who require endotracheal intubation without sedative medication. For example, patients in full cardiac arrest.

E) Patients with a known allergy to ketamine or etomidate.

F) Any individual wearing a MedAlert bracelet indicating that he/she has formally opted out of the EvK trial. These bracelets are discussed below.

9. Sources of Research Material:

The EvK Trial will be conducted at Parkland Memorial Hospital. The physical location of patient enrollment in this trial will include any location in Parkland Memorial Hospital where

patients require emergency endotracheal intubation, including the hospital floors (medical and surgical), specialty and sub-specialty areas, operating rooms, procedural areas, emergency department, intensive care units, and elsewhere in Parkland Memorial Hospital. The sources of research material are the patient lists maintained and used by the supervising medical and surgical teams. After enrollment in the EvK Trial, data will be gathered retrospectively through the EPIC electronic medical records system. No new clinical data will be generated in the patient's chart, other than documentation related to notification of study enrollment, which is mandated by the FDA. Eligible patients will be identified by the treating medical and surgical teams who are collaborating in the EvK Trial (see Page 1 and Appendix 2), as well as their colleagues who have been briefed on trial procedures, inclusion/exclusion criteria, and other aspects of the trial. An initial list of list of Co-Investigators is included on the front page of this protocol, and a list of study liaisons is attached in Appendix 2. The final list of Co-Investigators is likely to include additional individuals who work at Parkland Memorial Hospital and are employed by either Parkland Memorial Hospital or UT-Southwestern Medical Center.

10. Recruitment Methods and Consenting Process:

Study subjects will be recruited by the supervising medical and surgical teams, including the Anesthesia Code Team. Eligible patients will be screened using the inclusion and exclusion criteria. The patients enrolled in the study may include individuals under the direct care of the study investigators. For this clinical trial it is not possible to obtain written informed consent prior to patient enrollment. The U.S. Food and Drug Administration (FDA) published regulations regarding this type of research. These regulations are available in FDA 21 CFR 50.24. We will formally request to waive pre-enrollment consent. Based on FDA 21 CFR 50.24, we have crafted a comprehensive Community Consultation Plan and Post-Enrollment Notification Plan, which is

attached in Appendix 5. For participants who are screened but found not eligible for the study:

No data will be collected on these individuals. For participants who are screened and then enrolled in the study: The essential documents will be filed with each individual's research file, which will be maintained in secure storage.

11. Potential Risks:

The principal medical risks of this study relate to the side effect profiles of ketamine and etomidate. Both etomidate and ketamine are standard-of-care medications for emergency endotracheal intubation (Jabre et al., 2009). Each drug does have the potential for side effects, which include the effects listed below.

Common adverse reactions to etomidate

- A) Transient venous pain on injection
- B) Transient skeletal movements
- C) Hypoventilation
- D) Hypertension (uncommon) or hypotension (uncommon). Significant changes in blood pressure are relatively uncommon with etomidate.
- E) Nausea and/or vomiting
- F) Suppression of adrenal function

Common Adverse reactions to Ketamine

- A) Hallucinations, delirium
- B) Hypertension (more common, tends to be relatively minor changes) or hypotension (rare)
- C) Hypoventilation
- D) Tachycardia (usually minor)
- E) Nystagmus (involuntary eye movements)

As with any clinical research trial, there is a risk of loss of privacy with this study. We have a comprehensive strategy to mitigate that risk. That strategy is discussed below in Section 13.

12. Subject Safety and Data Monitoring:

Study oversight will include a Data Safety and Monitoring Board (DSMB). The DSMB will include specialists from several different specialties including anesthesiology, critical care medicine, surgery and pharmacy (Appendix 2). The DSMB will meet quarterly or monthly as needed to review all patient enrollments. If necessary the DSMB will meet more often than that to review specific study subjects. All study subjects will be reviewed by the DSMB for any study-related adverse outcomes. A written record of DSMB meetings will be generated. The IRB will be notified in writing of any adverse study-related outcomes, using the existing IRB reporting forms.

13. Procedures to Maintain Confidentiality:

Study data will be collected and stored at Parkland Memorial Hospital. Dr. [REDACTED] office in the Department of Anesthesiology will serve as the central node of the study. Her office is locked, and a locked storage cabinet will be used to store study-related materials. Her office is New Parkland Hospital, Rm# [REDACTED].

While the study is ongoing, electronic study data will be stored on a password-protected laptop computer, and on a password-protected flash drive(s). Study data itself will be maintained on a Microsoft spreadsheet file(s) that are maintained on secured computer devices, and on handwritten worksheets. The spreadsheet itself will include the study subject's medical record number and birthdate, along with other data relevant to the primary and secondary study endpoints. The study worksheets will include a patient demographic sticker. Appendix 3 contains

a sample data collection spreadsheet. Appendix 4 contains a sample study worksheet. These worksheets will be used to ensure proper follow-up with each study subject. Each subject will be given a study number, for example Subject001. Prior to public disclosure of data (for example publication of study results), all protected health information including medical record number and birthdate will be removed. For the sake of posterity, a confidential file will be maintained that links subject number to medical record number. This information will not be disclosed publicly. Study data will also be stored on a secured RedCap Database, a sample of which appears in Appendix 3.

Paper records that are generated during the study will include individual study subject worksheets (Appendix 4) which we will retain in secure storage, and also formal notification letters that will be placed in the medical record and/or mailed to enrolled patients and/or their families or next of kin (Appendix 13 and 14). Other paper documentation will include records of DSMB meetings. Paper records will be stored temporarily in [REDACTED] office in the locked storage cabinet.

Long-term storage of study data and forms will be in the Department of Anesthesiology storage locker. This locker is located [REDACTED]. The locker is climate controlled. The physical address is [REDACTED]. The key to the storage locker is maintained in the lock box in the Chairperson's Office Suite. This locker is used for long-term storage of clinic records, confidential files and other sensitive documents. We have used this storage locker for long-term storage of other research documents (with IRB approval). Once the mandatory storage time has elapsed (historically 6 years), study records will be destroyed.

The research team will have access to the study records and data. No one outside the research team will have access to protected health information, with the exception UT-Southwestern IRB, Parkland Hospital OCR, and any applicable state and federal oversight agencies. We anticipate publishing the results of our study in a medical or scientific journal, and/or on the internet. Anonymous study data, for example survival curves, study outcomes, and anonymous demographic data will be published as part of the report of study results. No PHI will be disclosed. We will also publish our methodology, including the methodology used for emergency research (Appendix 5). There will likely be several publications that arise from this research project.

14. Potential Benefits:

The purpose of this study is to define which agent, etomidate or ketamine, is associated with a greater chance of survival after emergency endotracheal intubation. We believe that the increase in the usage of ketamine that will happen as a result of this study is likely to benefit the patients at Parkland Hospital directly. In our recent QA/ QI project of emergency endotracheal intubations done by the Anesthesia Code Team (ACT) we found that etomidate is commonly used for sedation during this procedure. Propofol is also relatively commonly used by the ACT. However, in our review of cases we found that etomidate seems to be associated with lower long-term survival compared to other agents (Figure 3). In our QA/QI project we also observed that propofol is associated with the phenomenon of immediate post-administration cardiac arrest, more than any other sedative agent. Thus, we believe that increase in usage of ketamine that will happen as a result of this study is likely to benefit the patients at Parkland Hospital directly. There are many other potential benefits to patients outside the study, and to society in general. Presently etomidate is frequently used for emergency intubation, locally, nationally and

internationally. The EvK Trial may clarify if this practice is best for patients, or if the use of etomidate should be restricted.

15. Biostatistics:

The study is designed and powered to have 80% power with 0.05 level of significance to detect a 10% difference in proportions survived at 7-days post endotracheal intubation. Based on the data from our QA/QI project, the proportions of patients survived are assumed to be 85% and 95% for the etomidate and ketamine groups, respectively. With these assumptions, n = 750 patients (etomidate n=375, ketamine n=375) will be needed to have 80% power. Assuming a 10% screen failures (individuals who were randomized, but then never intubated for clinical reasons), we anticipate n = 825 will be needed.

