representatives) will be made in writing. Appendix 8 contains a list of community leaders who will be invited to the initial outreach meeting. We plan to invite more than 300 individuals and organizations to the community meetings. This number compares favorably to prior reports of community notification plans, for example Salzman et al., 2007. In Salzman et al., 2007, a total of 127 individuals and organizations were invited to meetings, for a population zone of approximately 3.8 million (Minneapolis-St. Paul, the “Twin Cities”). We plan to invite more than 300 individuals and organizations for a population zone of approximately 6.5 million (Dallas-Fort Worth). In addition to formal meetings, the EvK Trial research team will also be available to meet with community leaders and community members on an as-needed basis. Appendix 9 shows a draft letter that will be sent to community leaders.

An initial outreach meeting will be scheduled with the aforementioned individuals or their representatives in Appendix 8. The background and rationale for the clinical trial will be discussed. The clinical trial feedback mechanisms will be presented. A written report of this meeting will be generated and sent to the UT-Southwestern IRB and the Parkland Memorial Hospital CRO.

EvK Trial Feedback Mechanisms

There will be multiple avenues for feedback during the community outreach prior to the start of enrollment. The web-based feedback mechanisms will continue for the duration of the study.

1. Telephone hotline and opt-out: 214-TBD-TTBD
2. Standard Mail: Dept. of Anesthesiology & Pain Management, University of Texas-Southwestern Medical Center [name]

3. Email: [contact]
4. Web-Site (online feedback form): www.evkclinicaltrial.org (or similar, yet to be established). A Spanish language version of this website will be created.

EvK Trial Opt-Out Provision

Any member of the community who wishes to “opt-out” of any possibility of participation in this clinical trial will be given a MedAlert bracelet. This will be provided free of charge. Individuals within the catchment area of Parkland Memorial Hospital wishing to formally opt-out may do so through the aforementioned feedback mechanisms.

General content of community notification (including meetings, advertisements, website)

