Following enrollment in the study, the study team will assess for the patient's ability to discuss the clinical trial. Given the nature of this study (emergency endotracheal intubation), it is exceedingly unlikely that the patient will be able to participate in any meaningful discussion of research immediately after enrollment. In the rare circumstance that the individual patient is able to participate in a meaningful discussion in a timely way, then the study team will discuss the nature of the research project, its goals and objectives and the study protocols. The study team will give a letter notifying the patient of his/her enrollment into their medical record (Appendix 13). This will be documented in the patient's study worksheet (Appendix 4), and will complete the notification process.

For a large percentage of patients enrolled in this trial, we anticipate that the patients will not be able to have a meaningful discussion about the study immediately after enrollment, and possibly not for many days after enrollment. In this case, the study investigators will attempt to contact the patient's surrogates, legal guardians or next of kin, either in person at the patient's bedside or by telephone. If the aforementioned parties can be reached, the EvK Trial team will discuss the nature of the research project, its goals and objectives and the study protocols. If the family, surrogates, legal guardians or next-of-kin can be reached in person at the bedside or by telephone, the notification process will be considered complete.

If the family, surrogates, legal guardians or next-of-kin cannot be reached in person or by telephone, the EvK Trial team will send a letter to the patient's last known physical address (Appendix 14). The letter in Appendix 13 will be sent in the event that the patient is alive. In the

event that the patient is deceased, the research team will send the letter in Appendix 14. All of this will be documented in the patient's study worksheet on the Study Worksheet (Appendix 4).

During the notification process we will verbally request permission to use the patient's anonymous data. If verbal permission is granted, we will document that. If permission is denied, we will remove the patient's data from the study (from the point of denial of permission onward). Following these efforts, the EvK Trial team will do one of the following:

1. Document successful notification of the patient or family.

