2. Document no response from attempts at bedside and telephone contact.

Summary of the Community Notification Plan for the EvK Trial

The EvK Trial is a prospective randomized study that will randomize patients under emergency circumstances to receive either etomidate or ketamine for emergency endotracheal intubation. Because of the nature of emergency intubation, obtaining written informed consent prior to enrollment in the EvK Trial is not possible. In order to comply with current FDA guidelines for non-consented emergency research (FDA 21 CFR 50.24), the Community Consultation Plan in this document presents a broad-based approach to notify community leaders and community members, using traditional media as well as online media and direct community meetings. Patients (or their next-of-kin) enrolled in the EvK Trial will be notified of enrollment in accordance with FDA guidelines. Individuals in the catchment area of Parkland Memorial Hospital who wish to avoid any possibility of participation in the EvK Trial will be given a free MedAlert bracelet indicating that wish.

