No. The EvK Trial collaborators do not have a financial stake in the outcome of the study. The study is primarily funded by the University of Texas-Southwestern Medical Center. Both medications used in the EvK Trial (etomidate and ketamine) are generic medications, and the study is not being done to market either medication. The EvK Trial is not a “for profit” study. No drug companies, or their agents or representatives, were involved in the design of this study, and none will be involved in the conduct of the study. Patients will not be billed or charged for study-related activities.

11. How do I contact the research team if I have questions or concerns?

- E. Telephone hotline and opt-out: 214-TBD-TTBD
- F. Standard Mail: Dept. of Anesthesiology & Pain Management, University of Texas-Southwestern Medical Center [name]
- G. Email: [contact]
- H. Web-Site (online feedback form): www.evkclinicaltrial.org (or similar, yet to be established).

12. I would like to formally “opt-out” of the study. How do I do that?

Individuals who live in the catchment area of Parkland Memorial Hospital in Dallas, TX may “opt-out” of the study. To do this, please request to opt-out using the contact information above. You will be sent a custom MedAlert bracelet indicating this choice. The bracelet will be sent to you free of charge by mail.

13. When and where are the community meetings?

Community Leader Meeting

Month, Date, Year, Room X, Parkland Memorial Hospital, X PM

Open to all community leaders and news media. Translator services available.

Please RSVP to [contact], or 214-TBD-TTBD

Open Community Meeting

Month, Date, Year, Room X, Parkland Memorial Hospital, X PM

Open to the general public and news media. Translator services available.

Please RSVP to [contact], or 214-TBD-TTBD

Open Community Meeting

Month, Date, Year, Room X, Parkland Memorial Hospital, X PM

Open to the general public and news media. Translator services available.

Please RSVP to [contact], or 214-TBD-TTBD

14. Is this study approved by an Institutional Review Board (IRB)?

The IRB has reviewed the study, and has given us permission to begin the Community Notification Plan. The results of that plan will be reviewed by the IRB once the plan is completed. At that point the IRB may, or may not, permit us to begin enrolling patients.

15. How long will this clinical trial take?

Approximately 2-3 years

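### Criterion F excludes only people wearing the opt-out bracelet, so someone whose opt-out the study team already holds can still be randomised

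*Combined protocol and SAP*

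**What the plan says.** Section 8, criterion F, excludes "Any individual wearing a MedAlert bracelet indicating that he/she has formally opted out of the EvK trial". Section 5 describes envelopes with the inclusion criteria and "exclusion criteria (Section 8) on the outside to facilitate rapid and accurate screening of patients". Under Sections 4 and 5 the Anesthesia Code Team or the Emergency Department team screens the patient and opens the envelope just before giving the sedative.

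The opt-out itself works differently. The Opt-Out Provision in Appendix 5 (stated in Section I and again in Section II) says: "Individuals within the catchment area of Parkland Memorial Hospital wishing to formally opt-out may do so through the aforementioned feedback mechanisms". Those mechanisms are a telephone hotline, standard mail, email and a website form. The same provision says that a community member who wants to opt out "of any possibility of participation in this clinical trial will be given a MedAlert bracelet". The Summary at the end of Appendix 5 says that people in the catchment area "who wish to avoid any possibility of participation in the EvK Trial will be given a free MedAlert bracelet indicating that wish". Question 12 of the draft website (Appendix 10) adds: "The bracelet will be sent to you free of charge by mail".

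Appendix 5, Section V, covers the period after enrolment. The patient or family is notified and asked for permission to use the data: "If permission is denied, we will remove the patient's data from the study (from the point of denial of permission onward".

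**The concern.** The exclusion turns on what the patient is wearing, whereas the opt-out is a request that the study team receives. The two can differ. A person whose bracelet is still in the mail has opted out but fails criterion F, and so does a person who has the bracelet but is not wearing it at the moment of intubation.

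The trial asks for a waiver of consent before enrolment (Section 10), and the opt-out is the route by which a person can refuse in advance. Randomising someone whose refusal is already on file is a failure of participant protection. A team that followed the protocol to the letter would not even record an eligibility deviation.

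There is also a smaller analytic consequence. The error may come to light only at notification, after randomisation and dosing, and refusal at that stage limits data use only from then on. An exclusion before randomisation avoids the problem.

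**Working it through.** No figure in the plan bears on this point, so there is none to reproduce. The check sets the relevant passages side by side.

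1. **Rule applied at the bedside.** Exclude if the bracelet is worn (Section 8, criterion F, as printed on the envelope under Section 5). Section 10 adds only that patients are screened against the inclusion and exclusion criteria.
2. **Group the opt-out is meant to protect.** Everyone who has opted out (Appendix 5, Opt-Out Provision).
3. **Order of events.** The request reaches the study team first, and the bracelet is mailed afterwards (Appendix 10, question 12). No delivery time is given. Between request and delivery the team knows of the refusal and the person cannot be wearing the bracelet.
4. **Outcome for each case, assuming the patient is otherwise eligible:**
   - opted out and wearing the bracelet: excluded, as intended;
   - opted out, bracelet not yet delivered: no exclusion applies, can be randomised;
   - opted out, bracelet delivered but not worn: no exclusion applies, can be randomised.
5. **Search for a second check before randomisation.** Criteria A to E do not mention opt-out. Sections 4, 5 and 10 describe no list, chart flag or name check.
6. **Search for a check after randomisation.** The message to the principal investigator in Section 5 reports the enrolment and includes no opt-out check. The study worksheet (Appendix 4) has fields for notification and for data safety and monitoring board (DSMB) review, but none for opt-out status. The review items listed for the DSMB (Appendix 5, Section IV) do not name opt-outs. Notification counts as complete once family or next of kin are reached (Appendix 5, Section V), so an opt-out made earlier by the patient might never surface.
7. **Handling of the data.** Section 15 analyses by intention to treat everyone who receives an induction agent and is intubated. No rule covers an opted-out person who was randomised in error.
8. **Size.** Let N be the number of opted-out people who come to emergency intubation and are otherwise eligible, and w the proportion of them wearing the bracelet. The number left unprotected by criterion F is N × (1 − w). The documents give neither N nor w, so the result cannot be computed and could be zero.
9. **Effect on the statistics.** None of the inputs to the sample size in Section 15 depends on N or w.

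**The case against.** The strongest reply is that the plan guarantees nothing. In both places the phrase about avoiding any possibility of participation describes what the person wants. What the plan undertakes to give is a bracelet that signals that wish. A reader might infer that a stated promise has been broken, and the text does not support that. What stands is narrower: the exclusion rule does not cover everyone the opt-out is offered to protect.

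A reader might also infer that a large share of opt-outs would be missed. Nothing in the documents supports any percentage. The delay in the mail is the only route to failure that the text itself shows. A lost or removed bracelet is plausible but not discussed.

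A third reply is that a bracelet suits the setting. The envelope is opened moments before sedation, and Appendix 5 describes unstable patients intubated soon after arrival. A name search is slower than looking at a wrist, and it fails if the patient's identity is unknown. The trial uses the electronic record only after randomisation, so no existing step before randomisation offers a place for a check. This stands as a reason to keep the bracelet as the main bedside signal. It does not justify making the bracelet the only ground for exclusion when the team already knows of the refusal.

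Appendix 5 also lists, as a regulatory stipulation, asking an available family member about objection within the therapeutic window. Section V of that appendix, however, describes contact only after enrolment, and a family member's objection is separate from the person's own opt-out.

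Finally, Figure 5, the workflow, is redacted and some pages were not available. It would go too far to say that no opt-out record exists anywhere. Sections 8 and 10 and the opt-out text of Appendix 5 are all present, and they mention none.

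**Conclusion.** The point holds as a gap between the exclusion rule and the opt-out it is meant to enforce. As written, a person who is known to the study team to have opted out, but who is not wearing the bracelet, meets no exclusion criterion and can be randomised. This follows from the wording of criterion F and the mailing step and needs no assumption about rates.

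The number affected cannot be estimated from the documents. Sample size, alpha, power and the primary test are unaffected. The documents do not support reading this as a breached guarantee or as a failure of known frequency. That no opt-out record exists is a conclusion from the visible text only, so it carries moderate rather than full confidence. The wording of criterion F itself is not in doubt. The change is worth making because it protects participants at small cost.

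**What to change.** - Reword criterion F, in Section 8 and on the envelope, along these lines: *any individual known to have opted out of the EvK Trial, by MedAlert bracelet or by the study's opt-out record*.
- Log each opt-out on receipt in a secure study record held under the Section 13 safeguards. Do not keep paper lists of identifiers with the envelopes, which would conflict with those safeguards.
- Where a chart exists and the IRB agrees, add an administrative flag in EPIC. Reconcile this with the statement in Section 9 that the trial adds no new clinical data to the chart apart from notification documents. An administrative flag is not clearly barred, but the text should say so.
- Keep the bracelet as the main bedside signal.
- Check each enrolment against the record at the existing contact with the principal investigator. This comes after randomisation, so it detects and reports errors and does not prevent them.
- State how the data of an opted-out person randomised in error are handled, consistently with the intention-to-treat statement in Section 15 and the data-permission rule in Appendix 5, Section V.

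The cost is a sentence in the criteria, a short log, and one added check at a contact that already takes place. The study would hold identifiers of people who declined to take part, which needs IRB wording. The record will not help when the patient's identity is unknown or there is no time to look.
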